9.4.2 ASN51 Pharmacokinetics

Pharmacokinetic analysis will be performed on the PK Analysis Set.

Plasma concentrations of ASN51 will be analyzed using noncompartmental methods to determine the relevant PK parameters. The ASN51 concentrations and PK parameters will be listed and summarized by study day (and timepoint, as appropriate) and dose group. Individual and mean concentration profiles over time will be provided by participant/dose group and study day.

Details on the PK analyses will be in the SAP that will be finalized before database lock. Any integrated analyses across studies, such as a population PK analysis will be presented separately from the main CSR.

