- e ASN51 should be taken once daily in the morning with or without food. The first dose should be taken at the clinic visit under supervision. Participants should be instructed to bring all study medication to the site at each indicated visit to assess compliance. For ET visit, no study intervention should be dispensed.
- f Whenever performed on the same day, cognitive and functional assessments (ADAS-Cog13, CDR-SB, and MMSE) are to be performed before procedures that may be stressful for participants (for example, MRI, PET, blood draw, or CSF sampling).
- g Any clinically significant changes from baseline in the physical examination should be noted as an AE.
- h "Screen Version" questionnaire will be administered at Screening. The "Since Last Visit" questionnaire will be administered at all subsequent visits.
- i Unscheduled laboratory tests may be performed at any time at the discretion of the Investigator if clinically indicated for a suspected AE.
- j Record date and times of sample collection on the Lab Requisition Form. Obtain within 12 weeks of all lumbar punctures to confirm coagulation status.
- k Weeks 4, 12, and 24 visits only: Participants will be contacted by telephone 1 day before scheduled PK sampling to remind them not to take trial intervention on the morning of their next visit, and to instead bring the dose to clinic to take under supervision. During the call, participants will be asked what time their study medication was taken that day, and the site is to record the last dose administration time prior to the PK sampling visit.
- Day 1, Week 4, Week 12, and Week 24 visits: A pre-dose ASN51 plasma sample will be taken. The actual time of dose administration in the clinic should be recorded in the participant's eCRF. A post-dose sample will also be obtained 1.5 to 4 hours after the participant takes the dose of trial intervention at the site and sites will record if the participant eats a full meal, as judged by the Investigator, within ± 2 hours of the dose administration.
- m Blood and CSF for biomarker storage and blood for pharmacogenomics will be obtained, unless collection and/or transportation of the sample is prohibited due to local regulations. At the Day 1 visit, participants must have completed the blood and CSF collection procedures before randomization.
- n The pharmacogenomic sample may be taken at a later visit if it cannot be collected at Day 1 Visit.

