2.2.2 Risk Summary

2.2.2.1 Intervention Risks and Mitigation

2.2.3 Overall Benefit: Risk Conclusion

3 OBJECTIVES AND ENDPOINTS

Objectives	Endpoints							
Primary								
To evaluate the safety and tolerability of daily doses of ASN51 as compared with placebo	Incidence and severity of AEs Changes from baseline in laboratory safety assessments (including clinical chemistry, hematology, urinalysis, and serum hormone markers), Changes from baseline in vital signs, 12-lead electrocardiograms, and physical (including neurological) examinations Changes from baseline in C-SSRS							
Key Secondary								
To evaluate the effect of daily doses of ASN51 as compared with placebo on the pathophysiology of early AD To evaluate the effect of ASN51 versus placebo in change from Baseline to Week 24 on the pathophysiology of early AD	Change from baseline through Week 24 in CSF pTau217 Change from baseline through Week 24 in CSF total tau protein Change from baseline through Week 24 in plasma pTau217							
Other Secondary								
To evaluate the effect of daily doses of ASN51 as compared with placebo on tau pathology in early AD	Change from baseline through Week 24 in MK-6240 tau PET signal							
To evaluate the pharmacokinetics of ASN51 in early AD	Trough (C _{min}) at steady state and maximum (C _{max}) concentration of ASN51 in plasma at steady state through Week 24							
Tertiary/Exploratory								
To evaluate the effect of daily doses of ASN51 as compared with placebo on the pathophysiology of early AD To evaluate the effect of ASN51 versus placebo in change from Baseline to Week 24 on biomarkers of early AD	 Change from baseline through Week 24 in biomarkers, including but not limited to: Plasma Phosphorylated tau 181, GFAP, Aβ42/40, NFL CSF Phosphorylated tau 181, microtubule binding region tau 243, GFAP, Aβ42/40, NFL, neurogranin 							

ct of daily doses of with placebo on in early AD Change from baseline through Week 24 in: CDR-SB score ADAS-Cog13 score MMSE score ADCOMS score						
com Baseline to cructure Change from baseline through Week 24 in volumetric brain MRI parameters (e.g., whole brain volume, lateral ventricular volume, and cortical thickness measures of certain brain regions)						
Extension Period						
-term safety and 1 in early AD The incidence and severity of AEs over the DB placebo-controlled and LTE periods of the study						

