4.2 Rationale for Trial Design

The 24-week DB Intervention Period of chronic administration of ASN51 in patients with early AD is appropriate to establish safety and tolerability of ASN51 at multiple dose levels as measured by changes in laboratory safety assessments (including clinical chemistry, hematology, urinalysis, and serum hormone markers), vital signs, 12-lead ECGs, Columbia-Suicide Severity Rating Scale (C-SSRS), and physical examinations (including neurological examination).

The 24-week DB Intervention Period is also of sufficient duration to perform a population PK analysis of trough (C_{min}) and peak (C_{max}) PK at steady-state, to observe initial changes in AD pathophysiology and pathology as measured by fluid biomarkers, and to observe initial changes in cognitive function as assessed by AD clinical outcome measures.

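### Steady-state Cmax is assigned to noncompartmental analysis of one post-dose sample per visit, so it is biased low by an unknown, possibly small, amount

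*Combined protocol and SAP*

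**What the plan says.** **Endpoint.** Section 3 (and the synopsis) lists as an other secondary endpoint the steady-state trough and the maximum "concentration of ASN51 in plasma at steady state through Week 24".

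**Sampling.** The Table 2 footnotes in Section 1.3 give two plasma samples per PK visit. Before the dose: "Day 1, Week 4, Week 12, and Week 24 visits: A pre-dose ASN51 plasma sample will be taken". After it: "A post-dose sample will also be obtained 1.5 to 4 hours after the participant takes the dose of trial intervention at the site". On food: "ASN51 should be taken once daily in the morning with or without food". The site records the clinic dose time, the previous day's dose time, and whether a full meal was eaten within 2 hours of dosing.

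**Analysis.** Section 9.4.2: "Plasma concentrations of ASN51 will be analyzed using noncompartmental methods to determine the relevant PK parameters". Then: "The ASN51 concentrations and PK parameters will be listed and summarized by study day (and timepoint, as appropriate) and dose group".

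**Population PK.** Section 4.2 describes the 24-week period as of "sufficient duration to perform a population PK analysis of trough" and peak concentrations at steady state. Section 9.4.2 mentions the model only as an example of integrated cross-study analyses, "such as a population PK analysis will be presented separately from the main CSR".

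**Where the details will be.** Section 9.4.2 puts PK details in the SAP. Section 9.7 puts PK analyses in reports outside the SAP, and the opening of Section 9 says this may be so.

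**The concern.** Noncompartmental Cmax is the largest concentration observed in the dosing interval. It is a fair estimate of the peak when several samples surround the peak. Here one post-dose draw, at any point in a 2.5-hour window, has to serve as the peak.

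Two things follow. The reported mean sits below the true mean Cmax. The reported spread combines real differences between participants with differences in when the sample was drawn relative to each participant's peak, which food may also shift. A reader of the study report would take a value labelled noncompartmental Cmax to come from a sampled profile.

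Section 4.2 points to a method that uses the actual sampling times and would largely avoid this. The section that assigns the analysis does not name it as the source of the endpoint.

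**Working it through.** **Plan's own figure.** The documents give no Cmax value, precision, time of peak or half-life, so there is nothing to reproduce. The direction can be settled; the size can only be bracketed.

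**Direction.** Let R(t) = C(t)/Cmax at time t after the dose. By definition R(t) ≤ 1, with equality only at the peak. One draw at a time spread over 1.5 to 4 h therefore averages below 1, whatever the half-life or peak time. Weeks 4, 12 and 24 each give one such draw and are summarised by study day, so repeat visits do not remove the bias.

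**Inputs from the plan.** Dosing interval τ = 24 h (once daily); one post-dose draw, 1.5 to 4 h.

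**Assumptions.** One compartment, first-order absorption, steady state; draw time uniform over the window; half-life 6, 12, 24 or 36 h; time of peak 0.5 to 6 h.

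**Formulas.** With ke = ln 2 / half-life and ka chosen to give the assumed peak time:

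- C(t) ∝ e^(−ke·t)/(1 − e^(−ke·τ)) − e^(−ka·t)/(1 − e^(−ka·τ))
- mean ratio = (1/2.5) × ∫ R(t) dt from 1.5 to 4

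**Worked cell: half-life 12 h, peak at 2 h.** ke = 0.0578, ka = 1.563, 1 − e^(−24·ke) = 0.75, and e^(−24·ka) is negligible.

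- C(2) ∝ 0.8909/0.75 − 0.0439 = 1.144 (the peak)
- C(1.5) ∝ 0.9170/0.75 − 0.0959 = 1.127, so R = 0.985
- C(4) ∝ 0.7937/0.75 − 0.0019 = 1.056, so R = 0.923
- Mean over the window: 0.974

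**Mean recorded / true Cmax:**

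| Half-life | peak 0.5 h | 1 h | 1.5 h | 2 h | 3 h | 4 h | 5 h | 6 h |
|---|---|---|---|---|---|---|---|---|
| 6 h | 0.784 | 0.848 | 0.910 | 0.955 | 0.971 | 0.927 | 0.870 | 0.827 |
| 12 h | 0.884 | 0.918 | 0.950 | 0.974 | 0.981 | 0.950 | 0.909 | 0.874 |
| 24 h | 0.940 | 0.957 | 0.974 | 0.986 | 0.989 | 0.970 | 0.945 | 0.924 |
| 36 h | 0.959 | 0.971 | 0.982 | 0.991 | 0.992 | 0.979 | 0.961 | 0.946 |

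- Full range 0.78 to 0.99; median 0.95; 26 of 32 cells are at or above 0.90.
- Peak inside the window (1.5 to 4 h): 0.91 to 0.99.
- Lowest single draw: 0.65 (half-life 6 h, peak 6 h, drawn at 1.5 h).

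**Spread from timing alone.** At half-life 6 h and peak 0.5 h, the same participant records 0.903 of true Cmax at 1.5 h and 0.676 at 4 h.

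**Sensitivity.** A half-life of 4 h with a peak at 0.5 h lowers the mean to 0.70. Adding assumed between-participant variation (log-SD 0.5 in ka, 0.3 in ke), with half-lives of 6 to 24 h and typical peaks of 1 to 3 h, gives geometric mean ratios of 0.84 to 0.98.

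**The case against.** **The bias may be trivial.** This stands. The low figures need a short half-life together with a peak at the edge of the assumed range. The sponsor had Phase 1 plasma data when setting the window and may have placed it around the peak. The text that might show this (Sections 2.2 and 6.2) is blank in the public copy.

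**Section 8.7 (Pharmacokinetics) cannot be seen.** This stands in part. Its body is absent from the available text, so it may say how Cmax is derived. Denser sampling there is unlikely, because the summary of changes ties the same 1.5 to 4 h sampling sentence to Sections 1.3 and 8.7.

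**Population PK is already planned.** This also stands in part. A reader might infer that Section 9.4.2 contradicts Section 4.2 or drops the model. It does neither: it moves the model to a separate report, and noncompartmental summaries can sit beside that. What is missing is a statement of which analysis supplies the Cmax endpoint. Deferral to the SAP does not settle this, because Sections 9, 9.4.2 and 9.7 differ on whether PK analysis belongs there.

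**Nothing depends on Cmax.** This stands for everything visible. Given the protocol's concern with PR prolongation, a reader might infer that an exposure-PR relation or an exposure margin would be distorted. No visible passage plans either. ECG data are summarised by dose group, and the discontinuation and stopping criteria do not use Cmax.

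**Conclusion.** The point holds as a minor one. With one post-dose draw per visit, a noncompartmental Cmax is biased low and carries sampling-time noise. The direction needs no assumption about half-life or peak time; it sets aside only assay error.

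The size rests wholly on assumed pharmacokinetics: a mean shortfall of about 1% to 22% over the range in the table (1 − 0.992 to 1 − 0.784), and about 1% to 9% if the peak lies inside the window (1 − 0.992 to 1 − 0.910). The documents do not support a claim that the bias is material.

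Nor do they support extending the criticism to Cmin. The pre-dose sample, taken before a supervised dose after a reminder call, observes trough directly.

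**What to change.** In Section 9.4.2, and in whichever document will hold the PK analysis details:

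1. Name the population PK model, using the recorded dose and sample times, as the source of the steady-state Cmax endpoint, in line with Section 4.2.
2. In the study report, label the raw post-dose value *observed concentration 1.5–4 h post-dose*, not noncompartmental Cmax.
3. Leave Cmin as the observed pre-dose concentration.
4. State once whether PK analysis details sit in the SAP or outside it, so that Sections 9, 9.4.2 and 9.7 agree.

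The cost is wording only: no added samples, visits or participants. The small downside is that the Cmax endpoint waits for the separate population PK report.

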9.5 Analysis of Exploratory Objectives

Analyses of exploratory biomarkers and efficacy endpoints will include difference between treatments in mean change from baseline to Week for additional CSF biomarkers (including but not limited to

Absolute values and changes from baseline will be summarized using descriptive statistics by visit (and timepoint) and by dose group. Supportive plots will be generated as appropriate.

Details will be specified in the SAP which will be finalized before database lock for the DB Intervention period.

9.6 Additional Safety Analysis

Described in Section 9.2 and further delineated in subsections below.

9.6.1 Physical Examination

Baseline physical examination will be summarized in a frequency table by body system to characterize the enrolled Safety Analysis Set. Shift tables will be presented for each body system showing the change from baseline in status between Normal/Abnormal at each assessment.

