8.3.1 Physical Examination

Complete physical examinations will be performed by the Investigator or designated licensed professional (MD, NP, RN, PA, or equivalent).

A complete physical examination includes general appearance; head, eyes, ears, nose, and throat; and cardiovascular, dermatologic, respiratory, gastrointestinal, musculoskeletal, and neurologic systems (include neurological assessment of cranial nerves, motor, sensation, coordination, reflexes, and gait).

Findings will be recorded as normal/abnormal for each parameter with additional description as indicated.

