A summary of AEs by relationship to study treatment will be presented in a table by incidence of occurrence. The relationships will be collected based on the Investigator's determination of likelihood that study treatment could have caused the event. The possible relationships are "Unrelated", "Unlikely", "Possibly," "Probably," and "Definitely." For the summary of relationships, the categories of "Possibly," "Probably," and "Definitely" will be combined to form a single category of "Related." In the AE relationship table, if a participant reports multiple occurrences of the same AE (at the PT within SOC level and at the SOC level), only the occurrence with the greatest causal relationship will be presented. AEs that are missing relationship data will be presented in the summary table as "Related" but will be presented in the data listing with a missing relationship.

Adverse Events Leading to Treatment Discontinuation

All AEs for which the action "Study treatment discontinued" is recorded will be tabulated.

Serious Adverse Events

The data for SAEs will be presented in a listing. If a sufficient number of SAEs are reported, the severity and relationship tables can be subsetted on the SAE subpopulation.

Death

The data for participant deaths, if any, will be presented in a listing.

Changes from baseline in clinical laboratory test values, physical and neurologic examination results, vital signs measurements, and 12-lead ECGs will be listed and/or summarized through the end of trial.

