12.1.2 Adverse Event

An AE is any untoward medical occurrence associated with the use of a drug in humans, whether or not considered drug related. The term "adverse event" could include any of the following events that develop or increase in severity during the course of the trial. Examples include:

- Any sign, symptom, or physical examination finding that worsens in nature, severity, or frequency compared to baseline irrespective of association with the condition under study
- Any clinically significant laboratory abnormality or laboratory abnormality that requires medication or hospitalization
- Reactions to IMP including those occurring as a result of an overdose, abuse, withdrawal
 phenomena, sensitivity, or toxicity
- Concurrent illness
- Injury or accident.

Conditions present prior to enrollment are considered Medical History. Pre-existing conditions should be reported as a TEAE if there is a change in the frequency, intensity, or the character of the condition.

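### If neurologic is one row, the Section 9.6.1 shift table cannot show a new neurological abnormality in a participant already abnormal at baseline, and no by-arm summary of new findings is specified

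*Combined protocol and SAP*

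**What the plan says.** Section 3 lists among the primary safety endpoints "Changes from baseline in vital signs, 12-lead electrocardiograms, and physical (including neurological) examinations". Section 8.3.1 gives the neurologic system as one entry in its list of systems, with the instruction to "include neurological assessment of cranial nerves, motor, sensation, coordination, reflexes, and gait", which is six components. It adds: "Findings will be recorded as normal/abnormal for each parameter with additional description as indicated".

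Section 9.6.1 then sets the tabulation: "Shift tables will be presented for each body system showing the change from baseline in status between Normal/Abnormal at each assessment". It does not define the body-system rows, and it specifies no count of new findings over the whole post-baseline period. Table 2 places the examination at Day 1, Weeks 4, 12 and 24, and early termination.

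Other provisions also bear on examination changes:

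- Section 9.2 says that changes from baseline in several safety measures, among them "physical and neurologic examination results, vital signs measurements, and 12-lead ECGs will be listed and/or summarized through the end of trial".
- The Schedule of Activities footnotes say: "Any clinically significant changes from baseline in the physical examination should be noted as an AE".
- Section 12.1.2 gives as an example of an adverse event "Any sign, symptom, or physical examination finding that worsens in nature, severity, or frequency compared to baseline", and adds: "Pre-existing conditions should be reported as a TEAE if there is a change in the frequency, intensity, or the character of the condition".

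**The concern.** A binary status per body system discards the detail that Section 8.3.1 says is recorded. Take a participant with an abnormal reflex at baseline who has abnormal gait at Week 12. In a single neurologic row this is abnormal at both times, the same entry as for a participant in whom nothing changed. If the reflex finding resolves as the gait finding appears, the entry is again the same.

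The trial enrols people aged 50 to 80. Exclusion criterion 21 removes clinically significant screening abnormalities that create undue risk, compromise interpretation or suggest another cause of dementia; it does not remove every abnormal finding. Some participants may therefore start with an abnormal neurologic status.

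The drug's target is in the brain and the neurological examination is named in the primary endpoint, so this is a table that a safety reader will look at. The neighbouring sections each go further. Sections 9.6.2 to 9.6.4 add a summary of potentially clinically meaningful changes for weight, vital signs and ECG. Section 9.6.5 adds a by-dose-group count of participants with at least one clinically significant laboratory abnormality. Section 9.6.1 has no counterpart.

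**Working it through.** **The plan's own safety figure.** Section 9.10 uses N = 21 per arm (26 × 0.8 = 20.8) and the rule of 3. The rate is 1/(21/3) = 1/7 = 14.3%. The probability of at least one occurrence is 1 − (6/7)^21 = 96.1%, which agrees with the stated figure of at least 95% at about 14%.

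**Participants who can show a new abnormality.** Let b be the share whose neurologic status is abnormal at baseline. The documents do not give b, so 10% to 50% is an assumed range. In a single neurologic row, only the n = 21 × (1 − b) participants who start normal can move from normal to abnormal. With n rounded to whole participants, the rule-of-3 rate is 3/n and the probability of at least one shift at a true rate of 1/7 is 1 − (6/7)^n.

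| b (assumed) | n at risk of 21 | 3/n | P(at least one) at rate 1/7 |
|---|---|---|---|
| 0% | 21 | 14.3% | 96.1% |
| 10% | 19 | 15.8% | 94.7% |
| 20% | 17 | 17.6% | 92.7% |
| 30% | 15 | 20.0% | 90.1% |
| 40% | 13 | 23.1% | 86.5% |
| 50% | 10 | 30.0% | 78.6% |

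**Whether the difference between arms also shrinks.** Take illustrative new-deficit rates of 20% on ASN51 and 5% on placebo, b = 30%, and the same risk whatever the baseline status. Of 26 randomized per arm, 26 × 0.7 = 18.2 start normal. Expected shifts are 0.20 × 18.2 = 3.64 and 0.05 × 18.2 = 0.91.

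- Among those at risk: 3.64/18.2 = 20% and 0.91/18.2 = 5%. The difference is still 15 points.
- Over all 26: 3.64/26 = 14% and 0.91/26 = 3.5%. The difference is 10.5 points, but only because the denominator includes participants who cannot shift. Section 9.6.1 specifies no such denominator.

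Under these assumptions the loss is in numbers at risk, and so in precision, and the rate difference among those at risk is unchanged.

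**The case against.** The strongest reply is that new neurological findings have other routes into the results. Section 9.2 names the neurologic examination separately. The adverse event route is broad: the worsening-finding example in Section 12.1.2 carries no clinical-significance qualifier, and a pre-existing condition that changes in character is to be reported. New abnormal gait in someone with a baseline reflex abnormality fits that definition. It would then be tabulated by system organ class, preferred term and treatment group, and adverse event incidence is itself a primary safety endpoint. A reader might infer from Section 9.6.1 that the examination is analysed only by this table, or that a participant abnormal at baseline can never register a new deficit anywhere. The documents do not support either inference.

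The backstops are still partial. The wording in Section 9.2 can be met by a listing alone, and a listing is not a comparison by arm. Adverse event capture relies largely on the investigator: the schedule footnotes turn on clinical significance, and Section 8.4.1 records changes in safety parameters where the investigator deems it appropriate.

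Two further points stand. The protocol does not say that the neurologic system is one row; the list in Section 8.3.1 suggests it, but Section 9 leaves detail to the SAP, and the text available here has no SAP provision that settles it. And the baseline prevalence is unknown: the exclusions for other neurological disease and the good-health criterion may keep it towards the low end of the assumed range.

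**Conclusion.** The point holds as a limitation of one table. If the neurologic system is a single row, the Section 9.6.1 shift table cannot show a new abnormality in a participant already abnormal at baseline, nor one deficit replacing another, and the protocol specifies no by-arm summary of new neurological findings.

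The size depends on the unknown baseline prevalence. Over the assumed range the effect runs from slight at 10% to roughly halving the number at risk at 50%. It applies to the shift table, not to adverse event counts or listings. A reader might infer that the table would understate a true difference from placebo; that follows only if shifts are divided by all participants, which the plan does not say.

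This is a low-severity, inexpensive improvement to the planned tables. It does not call the primary safety analysis as a whole into question, and the p-values are in any case descriptive.

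**What to change.** In Section 9.6.1, and in the SAP table shells, present neurological shift tables for each of the six components named in Section 8.3.1. Add, by arm, the number and percentage of participants with at least one component abnormal at any post-baseline visit that was normal at baseline. State the denominator for both: participants normal at baseline on that component for the shifts, and participants with at least one normal component at baseline for the any-time count.

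These tables still would not show worsening within a component that was abnormal from the start; that remains with adverse event reporting and the recorded descriptions.

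The cost is more table rows to produce and review. Section 8.3.1 indicates that the data are recorded per parameter. If the eCRF captures only the system-level status, up to six normal/abnormal fields are needed. Design, sample size and participant procedures do not change.
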